11.2.5 Overall Survival

The overall survival is defined as the time from the date of the first dose until the date of death due to any causes. For subjects who have not died or who are lost to follow-up or withdraw consent, OS will be censored at the date of the last contact.

The overall survival will be summarized descriptively using the Kaplan-Meier method for the Evaluable, All Treated and PP populations. The Kaplan-Meier estimate for the median, first and third quartiles will be determined along with 95% confidence intervals (CI). The Brookmeyer-Crowley method will be used for the confidence interval calculation. The Kaplan-Meier estimate of OS rate at landmark times including but not limited to 3, 6, 9, 12, 18, and 24 months will be summarized. The overall survival will also be summarized by status of post study treatment new anti-cancer therapy (Yes or No) for the All Treated population. The Kaplan-Meier Plot of OS will be provided for the Evaluable and All Treated population. Listing of OS will be provided using the All Treated population.

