#### **4.3 Rationale**

##### **4.3.1 Rationale for the Trial and Selected Subject Population**

With the approval and use of pembrolizumab in 1st line therapy for advanced melanoma, the options to continue deriving benefit from CPI treatment in 2nd line or further have been considerably limited if not eliminated altogether for patients with advanced melanoma. It is therefore of interest to explore whether sensitivity to CPI can be restored in 2nd line or further treatment by appropriate and effective stimulation of the patient's innate and adaptive immune system.

Pembrolizumab has also demonstrated clinical activity in subjects with metastatic TNBC. Study KEYNOTE-012 enrolled subjects with a variety of solid tumors, including a cohort of 32 subjects with metastatic or recurrent TNBC, an ECOG performance status of 0 or 1, and positive for PD-L1 expression. The median age was 50.5 years and most were heavily pretreated, in both the early and advanced settings (47% of subjects having received at least 3 lines of therapy for metastatic disease and 25% at least 5). In the 27 subjects who were evaluable for response, ORR was 18.5%, including 1 CR. Stable disease and progressive disease were reported in approximately 26% and 48% of subjects, respectively. The median time to response (TTR) was 18 weeks, and the median PFS was 1.9 months. The median duration of SD was 17 weeks, while median OS was 11.2 months (Nanda et al., 2016).

Study KEYNOTE-086 Cohort A enrolled a total of 170 subjects with centrally confirmed metastatic TNBC,  $\geq 1$  prior chemotherapy for metastatic disease, ECOG performance status of 0 or 1, and had pembrolizumab 200 mg every 3 weeks for up to 24 months. The median age was 54 years and 44% of subjects received at least 3 lines of therapy for metastatic disease. The ORR was 5% regardless of PD-L1 expression. Best overall response was 0.6% CR, 4% PR, and 21% SD. Median DOR was 6.3 months (range 1.2+ to 10.3+). Median PFS and OS were 2.0 months (95% CI 1.9-2.0) and 8.9 months (95% CI 7.2-11.2) respectively (Adams et al., 2017).

Though in KEYNOTE-012, 18.5% of the subjects with PD-L1+ TNBC experienced an objective response, further data from the Phase 2 KEYNOTE-086 study showed the ORR was approximately 5% regardless of PD-L1 expression. These data highlight the need for further improvements in pembrolizumab-based combination immunotherapy.

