All subjects will receive Imprime PGG and pembrolizumab. Imprime PGG will be administered IV at a dose of 4 mg/kg over a 2-hour infusion time period on Day 1, Day 8, and Day 15 of each 3-week cycle for subjects at stage 1. If Stage 1 proceeds without safety concerns necessitating a second cohort at 2 mg/kg, Imprime PGG will be administered to the Stage 2 subjects at a dose of 4 mg/kg IV over a 2-hour infusion time period on Day 1, Day 8, and Day 15 of each 3-week cycle. If enrollment into an additional cohort for 2 mg/kg in Stage 1 is required and dosing proceeds to Stage 2, Imprime PGG will be administered in Stage 2 at a dose of 2 mg/kg IV over a 2-hour infusion time period on Day 1, Day 8, and Day 15 of each 3-week cycle. The pembrolizumab fixed dose of 200 mg will be administered IV over 30 minutes on Day 1 of each 3-week treatment.

Subjects will be dosed until disease progression, death, 2 years of treatment or study completion, whichever occurs first. After treatment discontinuation, subjects will be monitored every 2 months for survival until death or study completion. Study completion is defined as the death of at least 70% of subjects or 3 years after the last subject's first dose, whichever occurs earlier.

Discontinuation of treatment may be considered for subjects who have attained a confirmed CR, who have been treated for at least 24 weeks, and who had at least 2 treatments with study medications beyond the date when the initial CR was declared. Subjects who then experience radiographic disease progression may be eligible for up to 1 year of additional treatment with Imprime PGG + pembrolizumab at the discretion of the Investigator if:

- No cancer treatment was administered since the last dose of pembrolizumab
- The subject meets the safety parameters listed in the Inclusion/Exclusion criteria
- The trial is open

Subjects will resume therapy at the same dose and schedule at the time of initial discontinuation. Response or progression in this resumed course of therapy will not count towards the ORR of the primary endpoint in this trial.

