5.3 Final Analysis

The final analysis will be conducted after study completion. Study completion is defined as the death of at least 70% of subjects or 3 years after the last subject's first dose, whichever occurs earlier. Overall survival data will be included in the final analysis.

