9.3 Imputation of Partial Dates

Partial dates in selected datasets as specified below will be imputed. Imputed partial dates will not be used to derive the study day, duration (e.g., duration of adverse events), or elapsed time variables. However, imputed dates may be used as temporary variables for the purpose of sorting data in the listings. In addition, partial dates may be imputed for ‘slotting’ data to specific study time periods. Imputed dates will not be displayed in the listings.

The partial date will be included in the dataset with the imputed date and a flag variable to indicate the level of imputation. The flag variable can contain the values: blank and 'D'.

Blank: indicates that no imputation is done

D='Day': indicates that the day portion of the date is imputed

Start dates for the new anti-cancer therapy after the study treatment discontinuation will be temporarily imputed in order to define the event and censoring rules for PFS and duration of response. Dates will only be imputed when a month and year are available but the day is missing. The following rules will be used to impute the date when partial start dates are present on the post-treatment new anti-cancer therapy dataset:

Table 1: Rules for Imputation of Partial Dates

Dataset	Date	Missing Element	Rule
Anti-Cancer Therapy	Start Date	day, month, and year	No Imputation for completely missing dates
		day, month	No imputation for missing day and month
		day	If the partial date falls in the same month as the last dose of the study treatment, then assign to earlier of (date of last dose of study treatment+1, last day of month). If the partial date falls in the same month as the subject’s last radiological disease assessment and the subject’s last assessment is PD, then assign to earlier of (date of PD+1, last day of month). If both rules above apply, then assign to the later of the 2 dates. If the partial date falls in the months after the month of last dose of study treatment or last radiological assessment of PD, impute the missing day to the first day of the month.

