A summary of the assignments for event and censoring dates for PFS are specified in the following Table 3.

Table 2: Assignments for Event and Censoring Dates for PFS Analysis

Situation	Date of Event (PD/Death) or Censoring	Outcome
No (or inadequate) baseline tumor assessments and the subject has not died (if the subject has died follow the rules for death indicated at the bottom of the table)	Date of the first dose	Censored

Situation	Date of Event (PD/Death) or Censoring	Outcome
No adequate post-baseline assessments of CR, PR, SD or PD, and the subject has not died (if the subject has died follow the rules for death indicated at the bottom of the table)	Date of the first dose	Censored
Progression documented before death or without death	Date of assessment of progression	Event
No progression (or death)	Date of last adequate assessment of CR, PR or SD (on or prior to starting new anti-cancer therapy)	Censored
New anti-cancer treatment starting prior to documented disease progression	Date of last adequate assessment of CR, PR or SD (on or prior to starting new anti-cancer therapy)	Censored
Death before assessment of PD or before any adequate assessment of response	Date of death	Event
PD or death after missing one scheduled assessment	Date of PD or death	Event
PD or death after missing two or more scheduled assessments	Date of last adequate assessment of response of CR, PR or SD (prior to the missed assessments)	Censored

The primary analysis of PFS will be based on the radiological assessment, and the sensitivity analysis of PFS will be based on the radiological and clinical assessment. The PFS based on radiological assessment and PFS based on the radiological and clinical assessment will be summarized descriptively using the Kaplan-Meier method for the Evaluable, All Treated and PP populations. The Kaplan-Meier estimate for the median, first and third quartiles will be determined along with 95% confidence intervals (CI). The Brookmeyer-Crowley method will be used for the confidence interval calculation. The Kaplan-Meier estimate of PFS rate at landmark times including but not limited to 3, 6, 9 and 12 months will be summarized. The Kaplan-Meier Plot of PFS will be provided for the Evaluable and All Treated population. Listing of PFS will be provided for the All Treated population.

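### Minor: SAP 11.2.5 splits OS from first dose by later anti-cancer therapy, so the Yes and No curves would differ even if that therapy did nothing

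*SAP*

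**What the plan says.** SAP 11.2.5 sets time zero: "The overall survival is defined as the time from the date of the first dose until the date of death due to any causes". It plans descriptive Kaplan-Meier summaries for the Evaluable, All Treated and Per-Protocol populations, and adds: "The overall survival will also be summarized by status of post study treatment new anti-cancer therapy (Yes or No) for the All Treated population". No test, hazard ratio or statement of effect is attached to the split. The landmark times named in the same section are only time points at which Kaplan-Meier OS rates are read off. They do not define the Yes and No groups.

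The status arises late. New therapies are recorded during survival follow-up (Protocol 5.6.2 and 7.4.3) and listed with their start dates (SAP 10.5). Study treatment can itself run for a long time: "Subjects will be dosed until disease progression, death, 2 years of treatment or study completion, whichever occurs first". OS is reported in the final analysis after study completion (SAP 5.3).

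For PFS the SAP does treat new therapy as something that happens in time. SAP 11.2.4 has a censoring row for "New anti-cancer treatment starting prior to documented disease progression". The OS split has no comparable rule and, in the text available, no caution on interpretation. The split is not among the efficacy analyses in Protocol 9.1.3.

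**The concern.** The groups are defined by an event that follows time zero. Time from first dose to the start of new therapy is guaranteed survival for every Yes subject, while a subject who dies during that time is No by construction. This favours Yes. Subjects who respond for a long time and need no new therapy also sit in No, which pulls the other way. The groups thus differ in survival and progression history whatever the later therapy does.

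What is at stake is how one display is read. Two OS medians labelled by later therapy invite comparison, and in a cohort whose reference median OS is 8.9 months the built-in gap can be large.

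**Working it through.** The plan states no figure for this display, so there is none to reproduce. That the artefact exists follows from the definitions. The calculations below only size it, always with a later therapy that has no effect on survival.

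**Inputs from the documents.** For the cited pembrolizumab monotherapy study in pretreated TNBC, Protocol 4.3.1 reports: "Median PFS and OS were 2.0 months (95% CI 1.9-2.0) and 8.9 months (95% CI 7.2-11.2) respectively". The end of follow-up comes from SAP 5.3: "Study completion is defined as the death of at least 70% of subjects or 3 years after the last" subject's first dose. No such medians are given for melanoma, so that cohort is not sized.

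**1. A case that can be checked by hand.** Assume that:
- survival is exponential with median 8.9 months, λ = ln 2/8.9 = 0.0779;
- new therapy would start at 1 month plus an exponential time with median 2 months, μ = ln 2/2 = 0.3466, independent of survival;
- uptake is 75%.

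Then:
- P(Yes) = 0.75 × e^(−λ) × μ/(μ+λ) = 0.75 × 0.925 × 0.817 = 0.567.
- With a = μ+λ = 0.4245, survival in Yes for t > 1 is S_Y(t) = [a·e^(−λ(t−1)) − λ·e^(−a(t−1))]/(a−λ). At t = 12.5 this is 0.498, so the Yes median is about 12.5 months.
- Survival in No is S_N(t) = [e^(−λt) − P(Yes)·S_Y(t)]/[1 − P(Yes)]. At t = 4.1 this is (0.727 − 0.567 × 0.902)/0.433 ≈ 0.50, so the No median is about 4.1 months.

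The gap is 12.5 − 4.1 = 8.4 months with no true effect. Simulation gives the same medians. With uptake of 50-100% and median start times of 2-6 months (plus the 1 month), the gap is 6.0 to 11.8 months.

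**2. A more realistic case, with therapy tied to progression.** Assume that:
- PFS is exponential with median 2.0 months;
- 5, 10 or 20% of PFS events are deaths;
- post-progression survival is exponential with median 6.2, 6.8 or 8.4 months respectively, chosen so that median OS is 8.9;
- uptake is 50-90%, starting on average 1 month after progression;
- accrual is uniform over 12 months;
- follow-up ends at 70% deaths, applied to TNBC alone, or at 36 months after the last first dose.

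With 0-5% durable responders the Yes-minus-No gap in median OS is about +1.5 to +9 months. At 70% uptake, 10% deaths and no durable responders, the display would show about 10.7 against 6.3 months.

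**3. Could durable responders in No reverse it?** Protocol 4.3.1 gives a median duration of response of 6.3 months, and a median time to response of 18 weeks in the other cited TNBC study. Since 18 × 7/30.4375 = 4.1 months, the sum is 10.4 months. With 21% durable responders (the TNBC design alternative) and the same 1-month lag:

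| Median PFS of durable responders (months) | Yes-minus-No gap (months) |
|---|---|
| 6.3 | +1.5 to +8.6 |
| 10.4 | +0.9 to +8.1 |
| 12 | +0.6 to +7.8 |
| about 24 or more | negative in part of the assumed range |

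**4. What a landmark grouping removes.** Group subjects alive at month 6 by therapy started by then, and count OS from month 6. In the model of step 1 both medians become 8.8-9.0 months, and over all scenarios run the gap is 0.2 months or less. Guaranteed survival is gone.

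The model of step 2 shows what remains. With no durable responders, 2^(−6/2) = 12.5% of subjects are still progression-free at month 6, and nearly all of them are No. Because exponential PFS has no memory, their remaining median OS is 8.9 months, against 6.2 to 8.4 for progressed subjects. The landmark gap can therefore lean towards No by at most 8.9 − 6.2 = 2.7 months, and by more with durable responders.

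**The case against.** The strongest reply is that nothing is inferred. The split is descriptive, and survival by later therapy can serve as plain context for a single-arm OS curve. This stands, and it is why the point is minor. A reader might infer that the SAP offers the split as evidence of an effect of later therapy; it does not.

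A reader might also infer that the report would leave the artefact impossible to disentangle. That goes too far. The SAP plans listings of OS, PFS, date of last dose with reason for discontinuation, and later therapy with start date (SAP 11.2.5, 11.2.4, 10.1 and 10.5). With about 29 and 41 subjects, someone using those listings could see who died before starting new therapy. The summary display alone does not show it.

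A third tempting reading is that the sign of the gap is arbitrary. Step 3 does not support this for durations near the documented ones. The cited duration of response includes censored values and the combination might do better, but 24 months or more is an assumption.

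Finally, the display list that SAP Section 11 refers to as Section 15.2 is not in the text available, so a footnote there cannot be ruled out.

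**Conclusion.** The concern holds as a minor one. The OS split uses a status acquired after time zero, so the Yes and No curves would differ with an inert later therapy. For TNBC the built-in gap is about +1.5 to +9 months in favour of Yes with 0-5% durable responders. That range rests on the cited medians and on assumed uptake, lag, share of PFS events that are deaths, accrual and data cut. Durable responders in No can shrink the gap. At the 1-month lag they reverse it only if their median PFS is about 24 months or more. The size is illustrative; the existence of the artefact does not depend on the model.

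The effect stops at this display. A reader might infer that OS as a whole or the primary result is compromised. The documents do not support that: all-subject OS does not use the grouping, and the ORR test does not involve OS.

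**What to change.** Delete the sentence that splits OS by later therapy. In its place, report the number, type and timing of later anti-cancer therapies, using data already recorded under Protocol 5.6.2 and 7.4.3 and listed under SAP 10.5. The cost is one sentence and a simple table.

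If a split is wanted, use a landmark classification: take subjects alive and in follow-up at a prespecified time, group them by whether new therapy had started by then, and count OS from that time. Add a footnote saying that status is acquired after first dose, that selection of fitter subjects remains, that No still includes subjects who have not progressed, and that the display does not estimate an effect of later therapy. The day-missing rule in SAP 9.3 is written for PFS and duration of response, so state that it also applies to this grouping.

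The cost is one reprogrammed display. Subjects who die or are censored before the landmark drop out of that display only.

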11.3 Exploratory Efficacy Analysis Based on irRECIST

Exploratory efficacy analysis based on irRECIST may be run, including but not limited to analysis of ORR and PFS based on irRECIST. The irRECIST will be performed to confirm PD once PD is determined based on the RECIST 1.1. The following are scenarios where PD is confirmed based on irRECIST:

- Target lesions resulting in initial PD remains $\geq 20\%$ and at least 5 mm absolute increase compared to nadir sum of lesion diameters
- New PD due to target lesions sum of lesion diameters $\geq 20\%$ and at least 5 mm absolute increase compared to nadir
- Non-target lesions resulting in initial PD is worse (qualitative)
- New unequivocal PD of non-target lesions
- New lesion resulting in initial PD is worse (qualitative)
- Additional new lesion(s) since last evaluation

The PD confirmation status based on irRECIST will be collected in the CRF.

11.3.1 ORR Based on irRECIST

The best response based on irRECIST is the best response recorded from the start of study treatment until the disease progression (the PD per RECIST1.1 or the PD confirmed by irRECIST, whichever is later) or start of new anti-cancer therapy, whichever occurs earlier. The best response will be determined programmatically in the same way as the best response based on RECIST 1.1 (Section 11.1) except the following:

- Confirmed PD is considered the best response when PD is documented and confirmed by irRECIST and a best response of CR, PR, or SD could not be established before documentation of PD. Clinical progression alone in the absence of radiological confirmation is not a progression event in this analysis.
- Unconfirmed PD is considered the best response when PD is documented but not confirmed and a best response of CR, PR, or SD could not be established before documentation of PD. Unconfirmed PD will be further categorized as PD with further assessment but not confirmed by irRECIST vs PD without further assessment to confirm.

The best response based on irRECIST will be summarized for the Evaluable, All Treated and Per-Protocol populations. Calculation of ORR and CRR based on irRECIST are the same as those based on RECIST 1.1 in Section 11.1. In the summary, ORR, CRR, DCR, the number (%) of subjects with the best overall response of CR, PR, SD, confirmation PD, unconfirmed PD, and NE will be included, and an exact 95% confidence interval will be computed for the rates of ORR, CRR and DCR.

Listing of PD based on RECIST 1.1 and whether PD is confirmed by irRECIST at next visit will be provided.

